	
To evaluate the impact of laparoscopic surgery on adhesion- related formation, we are planning to perform an update of the SCAR studies to recent years in which a large number of laparoscopic surgeries have been performed. Comparison of readmissions for adhesion- related complications after open and laparoscopic surgery will be made. The study will provide an estimate of the current burden of adhesion-related morbidity in Scotland, which could also serve as a model for the current burden in other European countries. Further such estimate can be used to model the impact of further implementation of anti-adhesion barriers on adhesion-related morbidity and healthcare costs in both Scotland and abroad.

3.1.08	
Provide a full, clear and concise outline of the proposal design, listing: data sources; sample size ; inclusion/exclusion criteria (eg involvement in trial/survey; health event, etc); relevant date range; need for identifiable or potentially identifiable data; requirement for a matched control cohort etc.
 
We intend to use the Scottish National Health Service record linkage capabilities. Inclusion criteria are all patients undergoing initial abdominal or pelvic surgery between June 2009 and June 2011. Selection will be made by OPCS-4 codes related to the admission. A list of relevant codes can be found in the appendix. We choose for these years to allow inclusion of an incident population in a time that laparoscopic surgery had already been implemented and that allows for 4 to 5-years of follow-up.
 
We will exclude patient who had had abdominal or pelvic operation in the 5 years before 2009, as pre-existing adhesions from this prior surgery might influence results. There are no further exclusion criteria.
 
For analyses patients will be grossly divided in three groups of anatomical location of the surgery: hindgut, female reproductive tract, and foregut or other. Within each group subgroups of laparoscopic and open procedures will be made.
 
We expect approximately 70,000- 100,000 patients to have had abdominal or pelvic surgery in the period June 2009- June 2011. Approximately 25,000 are expected to have had prior abdominal surgery in the previous 5 years. Thus, we expect an incident population of 45,000 to 75,000 to be included in the study.

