### 4.2 All Other Datasets / sources *Please read section 4.2 of the guidance*

Dataset/source Name	Data Controller (Organisation)	Original purpose compatible with proposal?
Scottish Morbidity Record (SMR01)	National Services Scotland	Yes
NRS Deaths	NRS	Yes
CHI Database	NHS Boards	Yes

How were individuals originally informed of the use of their data? (if known)

Project specific consent was impractical for this study because of large size of the survey group and patients are not contacted. However:

- a) no identifiable patient data will be disclosed
- b) the necessary linkage will be performed by data controllers from the NHS Scotland board, that already hold the data. After linkage the data will be anonymised.
- c) the medical research serves public interest as outlined under 3.1.07.

The final dataset for analysis will not hold data that could result in indirect identification.

For existing dataset/sources for which the data controller is not an NHSScotland board, please append evidence of the data controllers permission to use the data

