### 4.3 Data Variables *Please read section 4.3 of the guidance*

Dataset/source Name	Variable	Time Period/Range	Processing only?
Anonymised ID			
Scottish Morbidity Record (SMR 01)	CHI	2004- Dec 2016	Yes
Scottish Morbidity Record (SMR 01)	Date of admission	2004- Dec 2016	No
Scottish Morbidity Record (SMR 01)	Sex	2009- Dec 2016	No
Scottish Morbidity Record (SMR 01)	Age (Date of admission- birth date)	2009- Dec 2016	No
Scottish Morbidity Record (SMR 01)	ICD-10 codes	2009- Dec 2016	No
Scottish Morbidity Record (SMR 01)	OPCS-4 codes	2009- Dec 2016	No
Scottish Morbidity Record (SMR 01)	Duration since index operation (date of admission from readmission - date of admission from index operation)	2009- Dec 2016	No
Scottish Morbidity Record (SMR 01)	Details of operation - laparoscopic/ open	2009- Dec 2016	No
Scottish Morbidity Record (SMR 01)	End of follow-up (month) (Date of end of follow-up, typically June 2016; however some patient might not complete follow-up because of mortality or migration)	2004- Dec 2016	No
Scottish Morbidity Record (SMR 01)	Continuous Inpatient Stay	2009- Dec 2016	No
CHI Database	Migration Month / year	2004- Dec 2016	No

NRS Deaths	Patient alive or death by end of follow-up	2004- Dec 2016 (measured in months, no date provided)	No
------------	--	---	----

Please justify your need for identifiable or potentially identifiable variables:

Identifiable data is only needed during the processing of data. Data will be collected during a range of 5 years from index surgery. Patients with a relevant OPCS-4 code as listed in the appendix are selected, if no prior such operation was found in the five years previous to the index operation. Identifiable information, NHS number and birth date are needed during processing to select reoperations that are definitely or potentially related to adhesion in patients following their index surgery. After processing these data can be removed. Age is potential risk factor for adhesions and will therefore be calculated.

4.4	NRS/NHSCR Data Sources Please read section 4.4 of the guidance	
Complete this section if access to NHSCR is required, or if there is any National Records of Scotland involvement		
4.4.01	Does the proposal require access to NHS Central Registry as a sampling frame for cohorts?	No
4.4.02	Does the proposal involve flagging of individuals on the NHSCR for long term follow up?	Choose an item.

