## Appendix A – Reference lists for applicants

### 1. Examples of Existing Datasets and Data Sources

SMR 00 Outpatients	SMR 04 Mental Health
SMR 01 Inpatients and Day Cases	SMR 06 Cancer Registration
SMR 02 Maternity	SMR 11/SBR Neonatal/Scottish Birth Records
Scottish Drugs Misuse Database (SDMD)	Birth Registrations
A&E – Accident & Emergency	Stillbirth Registrations
PIS Prescribing Information	Death Registrations
CHSP-PS/CHSP-S/SIRS – Child Health Surveillance and Immunisation	SCI-DC
NHS National Service Scotland's Information Services Division (ISD) maintains a National Dataset Catalogue (NDC) containing details of all health and health related datasets that are held by ISD. The Administrative Data Liaison Service (ADLS) publishes further information on key NHSScotland datasets	

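### The look-back counts a patient as never operated on when no record is found, without requiring five observable years in Scotland before the index operation

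*Combined protocol and SAP*

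**What the plan says.** Section 3.1.08 states the exclusion: "We will exclude patient who had had abdominal or pelvic operation in the 5 years before 2009". The reason given is "as pre-existing adhesions from this prior surgery might influence results", and the section adds: "There are no further exclusion criteria". Section 4.3 restates the rule as a selection step: a patient with a listed OPCS-4 code is taken "if no prior such operation was found in the five years previous to the index operation". The two statements anchor the five years differently, one to 2009 and one to the index operation, and they need to be reconciled. The point made here applies under either anchor.

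Section 4.2 lists three sources: SMR01, NRS Deaths and the CHI Database. Only SMR01 supplies operations. From CHI, section 4.3 requests "Migration Month / year" for 2004 to December 2016. The one place that describes a role for migration is the end-of-follow-up variable, which notes that "some patient might not complete follow-up because of mortality or migration". Section 3.1.08 limits baseline characteristics to age and sex.

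Appendix A, a general list of example datasets, shows "SMR 02 Maternity" separately from SMR01. Maternity records are not among the sources requested.

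**The concern.** The rule does not separate two kinds of patient: those watched for five years with no operation recorded, and those who could not be watched for all of that time. Someone who moved to Scotland in 2009 and had an index operation in 2010 has about one year of observable history, yet is classified exactly like a patient with five clear years. If that person was operated on elsewhere in 2007, the adhesions that the exclusion is meant to remove stay in the cohort, and any later readmission is attributed to the index operation.

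This is the plan's only safeguard against prior surgery. With age and sex as the only baseline characteristics, prior surgery that the look-back misses cannot be adjusted for afterwards. Two results are exposed: the estimated burden of adhesion-related readmission and, if missed prior surgery differs by route, the comparison of open with laparoscopic surgery.

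**Working it through.** **Does the requested migration range cover the look-back?** Index operations run from June 2009 to June 2011 (section 3.1.08). Five years earlier is June 2004 to June 2006. Migration is requested from 2004, so the range covers the look-back for every index date. What is missing is a rule that uses it.

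**The plan's own figure.** Section 3.1.08 expects 70,000 to 100,000 operated patients, about 25,000 of them with surgery in the previous five years.
- 70,000 − 25,000 = 45,000 and 100,000 − 25,000 = 75,000, which reproduces the stated incident population.
- The subtraction assumes that all 25,000 are identified.
- The implied share with prior surgery is 25,000/70,000 = 35.7% or 25,000/100,000 = 25%.

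**Ceiling on patients wrongly retained.** The documents give no migration figure. Assume that a share m = 3% to 8% of operated patients arrived within five years of index, that they had prior surgery as often as everyone else, and that none of it is visible in SMR01.
- Missed patients = 25,000 × m: 25,000 × 0.03 = 750 and 25,000 × 0.08 = 2,000.
- Share of operated patients: lowest 750/100,000 = 0.75%, highest 2,000/70,000 = 2.9%.
- Share of the cohort, which grows by the missed patients: lowest 750/(75,000 + 750) = 1.0%, highest 2,000/(45,000 + 2,000) = 4.3%.

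**Allowing for partial look-back.** Arrivals do have some Scottish history. If arrivals and prior operations are both spread evenly over the five years (assumption), half of the window is unseen on average and the missed numbers halve.
- 375 to 1,000 patients.
- Share of the cohort: lowest 375/75,375 = 0.5%, highest 1,000/46,000 = 2.2%.

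**Effect on results.** Let c be the cohort share with unseen prior surgery and k their readmission rate relative to the others. A group's rate is multiplied by 1 + c(k − 1). With k = 2 (assumption), rates rise by 0.5% to 4.3% in relative terms. For open against laparoscopic with no true difference, the apparent ratio is (1 + c_open)/(1 + c_lap):
- equal shares: 1.00;
- 4.3% open, 1.0% laparoscopic: 1.043/1.010 = 1.03;
- the reverse: 1.010/1.043 = 0.97.

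Nothing in the documents indicates which of these applies.

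**The case against.** The strongest reply is that this is a small matter. A five-year window already leaves in everyone operated on earlier, so some residual adhesions are accepted by design. Recent arrivals are probably few, they have partial history, and no mechanism is given by which migration would differ by route. If it does not differ, the null ratio stays at 1.00. The application also requests only a migration month and year; it does not say that arrivals are recorded, and section 4.6 on CHI access is marked not applicable. All of this stands and limits the weight of the point. It does not supply the missing rule, and the restriction is inexpensive to run.

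A reader might infer something stronger: that women with a recent caesarean pass the exclusion because maternity records are not requested. The documents do not establish this. A caesarean is caught only if it is on the prior-surgery code list and is recorded in SMR01; a gap in either would let the woman through. The documents say nothing about where caesareans are recorded, Appendix A shows only that a maternity dataset exists, and the code list is not reproduced in the available text.

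Nor can a bias be computed from this. Assuming unseen caesareans in 15% of open and 5% of laparoscopic cases, with a doubled rate, gives 1.15/1.05 = 1.10. The same shares reversed give 1.05/1.15 = 0.91, and equal shares give 1.00. Shares assumed for women of childbearing age also cannot be applied to the whole female reproductive tract group: if half of that group is of childbearing age (assumption), the first ratio falls to 1.075/1.025 = 1.05.

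**Conclusion.** The point holds for migration. Eligibility rests on no record being found in SMR01, this is the only exclusion, and no rule requires five observable years. As written, a recent arrival with surgery elsewhere enters as incident, although a variable that might identify such patients is requested.

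The effect is probably small. With 3% to 8% recent arrivals, the ceiling is 0.75% to 2.9% of operated patients, or 1.0% to 4.3% of the cohort; with arrivals spread evenly it is 0.5% to 2.2% of the cohort. These figures rest on assumed residence shares and on arrivals having had prior surgery as often as other patients. The effect on rates also assumes a doubled readmission rate. Neither the size nor the direction of any bias between routes can be derived from the documents.

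The caesarean question is secondary and conditional: it is something to confirm, not a demonstrated defect.

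**What to change.** 1. Confirm with the data controller that the CHI migration variable records arrivals in Scotland as well as departures.
2. Count a patient as incident only if the migration data show no arrival in the five years before the index operation (since birth for children under five) and no prior listed operation is found. Alternatively, keep the present cohort and report readmission rates and the open-versus-laparoscopic comparison with that restriction as a sensitivity analysis. If arrivals are recorded, this uses a variable already requested, and the cost is a small loss of patients.
3. State whether caesarean is on the prior-surgery code list and whether SMR01 captures it. If either answer is no, repeat the female reproductive tract comparison in women aged 50 or over at index, using data already requested. That analysis is less precise and changes the case mix, so a different result could not be put down to caesareans alone. The other option is to ask for a processing-only yes/no flag from the maternity dataset, together with caesarean on the code list. That adds a source and needs its own justification, since section 3.4.02 relies on data minimisation and section 3.3.01 describes the current access as being for editors' questions on presentation.

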## Section 5 – Methodology & Data Processing

5.1	Methodology Please read section 5.1 of the guidance		
5.1.01	
Does the proposal require any of the following:
 
 Data  Single anonymised data extract
 
matching/linking
 
 Use of matched
 
controls
 
Other (please specify):
		
5.1.02	Who is carrying out any indexing/ linkage/anonymisation, and where?	Data controller - national Services Scotland (@Farr Institute)	
5.1.03	Which data sources listed at section 4.1 and 4.2 will NSS/NRS receive identifiers for linkage purposes?	Scottish Morbidity Record (SMR 01)	
5.1.04	
What variables will be provided for linkage?
 
 CHI Number  Forename  Surname
 
 Date of Birth  Address or Postcode  NHS Number
 
Other Please Specify:
		

5.2	Access Please read section 5.2 of the guidance		

Complete the following section if you answered 'No' to question 3.6.1
			
5.2.01	At what location is identifiable or potentially identifiable data being accessed?		
5.2.02	Please provide details of security policy/procedure governing access to this physical and technical environment – append supporting documentation		
5.2.03	Does this policy/procedure cover password policy in detail? Please provide details/ append supporting documentation		

5.2.04	Does this policy/procedure cover user account management, including review or removal of access to sensitive/personal data, in detail? Please provide details/ append supporting documentation	
5.2.05	Will individuals with access to data have individual or shared accounts?	
5.2.06	Will the data be accessed by staff working off site eg staff working from home at any time during the duration of the proposal?	Choose an item.
5.2.06b	If yes, are policies/procedures in place to facilitate, monitor and audit this access? Please provide details/ append supporting documentation	If applicable
5.2.07	Provide any additional detail of how data is protected from unauthorised access	If applicable

5.3	Store & Use Please read section 5.3 of the guidance	
Complete the following section if you answered 'No' to question 3.6.1		
5.3.01	Where is data being stored and used? (location, organisation, address – refer to addresses in previous sections if appropriate)	
5.3.02	Data Protection Registration Number	If applicable
5.3.03	ISO 27001 Cert. No.	If applicable
5.3.04	Please provide details of security policy/procedure governing storage and use of data within this physical and technical environment – append supporting documentation	
5.3.05	Does this policy/procedure cover the implementation of up-to-date controls for the detection and prevention of malware? Please provide details/ append supporting documentation	
5.3.06	Does this policy/procedure cover access control and auditing of system administrator activity? Please provide details/ append supporting documentation	

5.3.07	Does this policy/procedure cover the production of backups and the controls in place around these? Please provide details/ append supporting documentation	
5.3.08	Does this policy/procedure describe the controls in place to prohibit unauthorised copying of data? Please provide details/ append supporting documentation	
5.3.09	Does this policy/procedure describe physical and site controls? Please provide details/ append supporting documentation	
5.3.10	Does this policy/procedure cover hardware repair, replacement or disposal and protection of data from inappropriate access during such procedures? Please provide details/ append supporting documentation	
5.3.11	Describe the systems, software and security used to store and use data - please provide details/ append supporting documentation	
5.3.12	Is outsourced IT in use? Please give details	
Please repeat section 5.3 above for each relevant location in the proposal – see guidance		

5.4	Transfer Please read section 5.4 of the guidance	
5.4.01	Please provide details of security policy/procedure to ensure that data will be transferred in such a way that it is protected from inappropriate or unauthorised access (mention email encryption, secure file transfer protocols SFTP, device encryption, physical controls, etc, as appropriate) - append supporting documentation	Identifiable data will not be transported. Only results from statistical analyses will be downloaded through secure file transfer protocols while connecting to the safe haven. Downloaded data will be stored solely on computer at the Radboud University Medical Center, complying

		to its electronic safety protocols.
5.4.02	At what intervals/ trigger points will data transfer take place?	Analysed data will be transferred regularly, during a period of 4 months.
5.4.03	Will any identifiable or potentially identifiable data be transferred outside of the UK?	No
5.4.03b	If yes, please provide details of the country of destination, the method of transfer, the proposed location and method of storage outside of the UK, and details of any further onward transfer	If applicable
5.4.04	Other than initial transfers from source systems, is there any copying of data required within the proposal? Please give details	No

5.5 Dissemination Please read section 5.5 of the guidance		
5.5.01	Will proposal findings be published or disseminated beyond the proposal team?	Yes
5.5.01a	If yes, how will proposal findings be published or disseminated, to what audience and in what format? Please give details	Results will be published as a paper in a peer-reviewed medical journal. Results will further be presented at surgical conferences and congresses using powerpoint format.
5.5.01b	If yes, what steps will be taken to ensure that persons cannot be identified in published findings (eg disclosure control procedures (safe haven), use of aliases, numbers, avoidance of small geographical areas, avoidance of small numbers, etc)? Please give details	Graphs and tables in publications will provide only large nationwide number that is not identifiable.
5.5.01c	If yes, are there any circumstances where a living or dead individual would be cited? (eg where a person	No

	
consented to their data being used as a case study)?        Please give details
	
5.5.01d	If yes, were any permissions to publish data required or sought (for example from data controllers)? Please provide details	No

5.6	Retain/Dispose Please read section 5.6 of the guidance	
5.6.01	Which information/data/records retention policy will you be applying to the proposal data (details of the policy and the organisation to which it belongs)?	
5.6.02	How long do you intend to retain identifiable or potentially identifiable data after the conclusion of the proposal (including archive/backup copies)?	
5.6.03	Who will retain the data and where?	
5.6.04	What is the purpose for retaining the data for the specified time?	
5.6.05	What method of disposal or destruction will be used when this period has expired (including archive/backup copies)?	
5.6.06	What evidence will be obtained that destruction has occurred (eg IT supplier certificate of destruction, etc)?	

5.7	Review Please read section 5.7 of the guidance	
5.7.01	Describe how the mechanisms which safeguard data security will be audited and reviewed at regular intervals to ensure their continued efficacy	
5.7.02	Describe any resource implications to any of the proposed measures for the protection of physical or technical security of information which are unresolved at the time of this application? (for example encryption of devices is an intention not yet fulfilled, training is not yet undertaken, etc)	
5.7.03	Describe the breach reporting mechanisms to be invoked in the event of any inappropriate access to data or other information security incident	

## Section 7 - Supporting Evidence

### **Supporting Evidence** *Please read section 7 of the guidance*

Please list each piece of supporting evidence which you have included with your application in the box below – the name of each should clearly indicate what the document/file/reference is about

- Appendix with list of OPCS 4.7 and ICD10 codes relevant for selection of data
- Certificates of Research data and confidentiality training
- Protocol as send for IRB approval
- IRB approval
- Privacy Impact assessment

## Appendix A – Reference lists for applicants

### 1. Examples of Existing Datasets and Data Sources

SMR 00 Outpatients	SMR 04 Mental Health
SMR 01 Inpatients and Day Cases	SMR 06 Cancer Registration
SMR 02 Maternity	SMR 11/SBR Neonatal/Scottish Birth Records
Scottish Drugs Misuse Database (SDMD)	Birth Registrations
A&E – Accident & Emergency	Stillbirth Registrations
PIS Prescribing Information	Death Registrations
CHSP-PS/CHSP-S/SIRS – Child Health Surveillance and Immunisation	SCI-DC
NHS National Service Scotland's Information Services Division (ISD) maintains a National Dataset Catalogue (NDC) containing details of all health and health related datasets that are held by ISD. The Administrative Data Liaison Service (ADLS) publishes further information on key NHSScotland datasets	

